uterine smooth muscle cells. Food and Drug Administration (FDA) approved the application of rapamycin to treatment of moderate-severe LAM. Results of its clinical application showed that mTOR inhibitors brought landmark change to LAM patients. Before mTOR inhibitors were applied for treatment of LAM, lung transplantation was almost the only therapy for LAM. At present, application of mTOR inhibitors is the main clinical therapy for LAM with significant effects and high safety. Hence, the prospect of application of mTOR inhibitors to treatment of uterine fibroids is promising, especially for patients with symptomatic uterine fibroids or myomatosis who refuse or are not suitable for operative treatment. Thus, treatment with mTOR inhibitors may become the best long-term therapeutic schedule that can replace operative treatment for patients with uterine fibroids.

mTOR inhibitor rapamycin (sirolimus), is a new type of macrolide immunosuppressors. Initially, sirolimus was used as low-toxicity antifungal antibiotics. In 1978, it was found that it could realize immunosuppression of autoimmune diseases. In 1989, it was on trial as a new type of immunosuppressors against rejection of organ transplantation. In September, 1999, FDA formally approved its appearance on the market. So far, more than twenty countries have approved or registered it for prevention of acute rejection of patients receiving organ transplantation. Currently, there are 2082 clinical trials relating to rapamycin and 924 of them have been finished. In China, as a new drug of the second category, sirolimus was permitted to be used clinically in 2002. With 15-year clinical application, its safety data also show its favorable safety features without related security problems.

However, there's no application of mTOR inhibitor sirolimus to treatment of uterine fibroids yet and its curative effects and safety still need to be verified through rigorous clinical trials. Therefore, this study used sirolimus to treat patients with symptomatic uterine fibroids or myomatosis who refused or were not suitable for operative treatment, discussed its therapeutic value for uterine fibroids or myomatosis and provided a clinical basis for formulation of the best therapeutic schedule of non-surgical treatment for uterine fibroids or myomatosis.

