## IV. Research design

1. This study is a non-random open-label clinic trial carried out by the department of gynaecology and obstetrics, Peking Union Medical College Hospital.
2. All patients who accorded with inclusion criteria and signed informed consents received sirolimus treatment for at least three months. After drug withdrawal, there patients were followed up for at least one year.
3. There should be at least 25 patients included in this study without an upper limit of included patients.

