## VI. Therapeutic schedule

1. Initial dosage of administration and dosage regimen: take 2mg of sirolimus once a day since the fifth to seventh day of menstruation. After one week of medicine taking, subjects are called for an interview. If a subject has severe adverse reactions and fails to tolerate the drug, her weekly dosage can be reduced to 0.5mg, where the minimum daily dosage should be 1mg / day. If the subject still fails to tolerate the drug, she should quit; if she feel unwell but tolerable, the administration should be continued for another three months. After the three months, evaluate the condition of this subject.
2. Subsequent dosage of administration and dosage regimen: if the condition of a subject is significantly improved after taking 2mg of sirolimus once a day for three months, the initial administration should be continued. If the condition of a subject shows no significant improvement, the dosage should be changed into 2.5mg-3mg once a day. If this subject fails to tolerate the dosage, she should quit this study; if she can tolerate the dosage, this dosage regimen should be executed for three months. After that, her condition should be evaluated again.
3. Iron supplement: if hemoglobin of a subject  $\leq 10.9$  g/dL, she should receive iron supplement in accordance with the standard dosage regimen. However, the iron supplement is not regarded as a part of treatment of this study and will be recorded as a part of drug combination.
4. If the condition of a patient with a rare type of uterine fibroids (including intravenous leiomyomatosis, leiomyomatosis peritonealis disseminate and benign metastasising leiomyomas) is under control with a tolerable drug, the patient can continue this drug therapy after this six-month study.

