### 2. Evaluation during sirolimus treatment

In the first month of treatment, evaluation of adverse reactions is conducted every week. In the third and sixth months, curative effects and safety of sirolimus were assessed.

1) Evaluation of curative effects: sizes of the uterus and fibroids were measured through pelvic MRI. Blood was drawn to monitor the female hormone level and impacts of bleeding and symptoms on daily life of subjects.

2) Evaluation of safety: safety parameters (such as to enquire AE and measure laboratory values, vital signs, thickness of endometrium, abnormal uterine bleeding and sizes of follicular structure including follicle and functional ovarian cysts) are monitored periodically during the study.

3) Treatment compliance: in order to monitor compliance, subjects are asked to keep an E-diary every day. Researchers track each date of studied drug taking in accordance with E-diaries. In each interview, researchers and subjects examine the data integrity of E-diaries together.

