### 3. Evaluation after treatment

Evaluation of curative effects and safety is conducted at the end of the drug therapy, six and twelve months after the treatment, where the evaluation content is the same as that before the trail.

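### Rare-type patients who continue sirolimus after month 6 have no dated safety evaluation between month 6 and the end of therapy, and their study status in that time is not stated

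*Combined protocol and SAP*

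**What the plan says.** The relevant provisions of the combined protocol and SAP are these.

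- **Duration.** Section IV item 2 says that all patients "received sirolimus treatment for at least three months" and are then followed for at least a year after withdrawal. It sets no upper limit on treatment. Section VI item 4 adds, for controlled and tolerating patients with rare types, that "the patient can continue this drug therapy after this six-month study".
- **On-treatment evaluations (VIII.2).** "In the first month of treatment, evaluation of adverse reactions is conducted every week". Then: "In the third and sixth months, curative effects and safety of sirolimus were assessed". No later on-treatment date is given. Safety parameters also "are monitored periodically during the study", with no interval.
- **Later evaluations (VIII.3).** "Evaluation of curative effects and safety is conducted at the end of the drug therapy, six and twelve months after the treatment". These visits repeat the pre-treatment list of examinations.
- **General clauses.** Section X calls for adverse-reaction monitoring plans and a follow-up plan to be drawn up. Section XIV provides for expert safety supervision throughout the study. Neither names a visit or a date.
- **Analysis.** Section IX.1 summarises categorical data as counts and percentages. Section IX.2 assesses adverse events that occur while patients take the drug, with no time limit.

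**The concern.** The visit schedule has two clocks. One runs from the start of treatment and stops at month 6. The other runs from the end of treatment. A patient who continues under VI item 4 is past the last date on the first clock and has not started the second. A patient who stops at month 6 has dated evaluations 6 and 12 months later, while a patient who keeps taking the drug has none until she stops.

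This bears on the trial's own aims. Safety in the rare types is a stated objective (section II). The Background says safety in this use still has to be shown, and suggests that "treatment with mTOR inhibitors may become the best long-term therapeutic schedule". Section VI item 4 is the one clause that expressly permits treatment past the six-month period, so it is where longer-exposure data would be expected. The planned adverse-event analysis takes in this time, but the collection of events in it is not dated. The analysis would also report counts and percentages over patients whose exposure may be very unequal.

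**Working it through.** The plan states no figure on this point to reproduce. The check places every dated safety evaluation on one patient's timeline.

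**Inputs.** On-treatment dates from VIII.2; later dates from VIII.3, consistent with IV item 2; permission to continue from VI item 4. Treatment duration T is not given and is assumed below.

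**Step 1: dated evaluations for T > 6.** Weekly in month 1 (about 4), month 3, month 6, month T (end of therapy), T + 6 and T + 12. Up to and including month 6 that is 4 + 1 + 1 = 6. The number strictly between month 6 and T is 0, whatever T is.

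**Step 2: length of the gap, T − 6.**

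| Assumed T (months) | Gap without a dated evaluation | Dates after month 6 |
|---|---|---|
| 6 | 6 − 6 = 0 | 12, 18 |
| 12 | 12 − 6 = 6 | 12, 18, 24 |
| 18 | 18 − 6 = 12 | 18, 24, 30 |
| 24 | 24 − 6 = 18 | 24, 30, 36 |

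At T = 6 the month-6 and end-of-therapy evaluations coincide and there is no gap. The gap therefore comes only from continued treatment.

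**Step 3: do the general clauses supply a date?** The periodic monitoring in VIII.2 has no interval and is limited to the study, as is the supervision in section XIV. Section VI item 4 describes continuation as coming after a six-month study. Section IV item 2 and VIII.3, however, run the study on until at least a year after withdrawal. On one reading the continuing patient is outside the study; on the other she is inside it. The text does not choose, and on neither reading does it give a date.

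**Step 4: effect on the adverse-event summary.** Exposure up to month 6 is min(T, 6) and beyond it is max(T − 6, 0). With the three-month minimum, the split is 3 and 0 months. With an assumed T of 18, it is 6 and 12 months, a total of 18 / 3 = 6 times the minimum. A percentage of patients with an event treats these two patients alike; a rate per patient-month does not.

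**The case against.** **The study does not end at month 6.** Section VI item 4 may mean only the six-month treatment phase. Section VIII.2 is headed as covering sirolimus treatment and has no stated end, so the periodic monitoring and daily E-diary may continue. This is a fair reading, and it means monitoring cannot be called absent. What stands is that the interval is not stated and the patient's status is unclear.

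**If continuation is post-study care, the trial need not schedule it.** That is a legitimate design choice, but the plan does not state it. It would also sit awkwardly with section IV item 2, which follows all patients for a year after withdrawal.

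**The later visits may count from the end of the six-month study treatment.** They would then fall at about months 12 and 18. The wording of VIII.3 does not support this: its first evaluation is at the end of the drug therapy, and its heading concerns the time after treatment.

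**The flow chart is not shown.** Section VII has no readable content, so a schedule given only there cannot be ruled out. This caveat stands in full.

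A reader might also infer more than the documents support:

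- That these patients have no scheduled safety evaluation on the drug at all. They have those in month 1 and at months 3 and 6, and one when therapy ends.
- That the time after month 6 is unmonitored. The general clauses and routine care are not excluded; only dates are missing.
- That these patients are the trial's only source of exposure past six months. Section IV sets no maximum for anyone.
- That the number of affected patients, or the share of their exposure, can be computed. The plan gives neither the number continuing nor T.

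**Conclusion.** The point holds in a limited form. In the readable text, no safety evaluation is dated between month 6 and the end of therapy for a rare-type patient who continues under VI item 4. The gap is T − 6 months, with no stated bound because the plan sets no maximum T. Whether she remains a study subject, and whether the undated monitoring applies to her, is not stated.

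This is more than missing detail, because the rule as written dates evaluations after stopping and none during continued exposure. The conclusion rests on two conditions: that VIII.3 counts from the actual end of therapy, as its wording indicates, and that the flow chart does not show a further schedule. It does not establish that any harm would be missed. It deserves an amendment, since safety is an objective and the text change is small.

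**What to change.** 1. Check the flow chart in section VII. If it dates on-drug evaluations after month 6, carry them into VIII.
2. Reconcile VI item 4, VIII.2 and VIII.3. State whether a continuing patient remains a study subject. If she does not, say so and say how adverse events after month 6 are treated in the analysis.
3. If she does, tie her on-drug safety evaluations to dates that do not depend on stopping, with the safety content of VIII.2. The pre-treatment list that VIII.3 reuses does not name an adverse-event enquiry. One illustration of such an anchor is the existing VIII.3 intervals counted from month 6, giving 6 + 6 = 12 and 6 + 12 = 18; that alone would leave treatment past month 18 undated. The interval, the duration of treatment and all clinical management remain the sponsor's decision. The evaluations after stopping would stay as they are.
4. In IX.2, report adverse events per patient-month of exposure, separately up to and beyond month 6. The E-diary already records drug-taking dates; state that it is kept during continuation.

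The cost is a few sentences in VI, VIII and IX, additional visits for continuing patients (two each in the illustration, if treatment lasts that long), and slightly more analysis.

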## VII. Flow charts of research

## VIII. Follow-up plan and content

### 1. Evaluation before the trail

Each subject should complete the following items in four weeks before the treatment:

- 1) Complete medical history
- 2) Detailed personal profile
- 3) A physical examination
- 4) A blood routine examination
- 5) Examinations of hepatic and renal function and blood fat
- 6) A detection of female sex hormones between the second and fourth days of menstruation
- 7) A routine urine test + an urine pregnancy test]
- 8) A pelvic MRI inspection

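### The visible text names no pregnancy test between baseline and end of therapy, so the month-3 decision to continue or raise sirolimus does not require pregnancy to be excluded

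*Combined protocol and SAP*

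**What the plan says.** - **Baseline (VIII.1, item 7).** In the four weeks before treatment each patient has "A routine urine test + an urine pregnancy test". This is the only place where the visible text names a pregnancy test.
- **On treatment (VIII.2).** "In the third and sixth months, curative effects and safety of sirolimus were assessed". For efficacy, "sizes of the uterus and fibroids were measured through pelvic MRI", and "Blood was drawn to monitor the female hormone level". Safety monitoring is an open list: "such as to enquire AE and measure laboratory values, vital signs, thickness of endometrium", followed by abnormal bleeding and the size of follicular structures. No pregnancy test is named.
- **After treatment (VIII.3).** The baseline content is repeated when therapy ends and 6 and 12 months later, so the urine pregnancy test returns by reference.
- **Dose decision (VI.2).** A patient whose condition "is significantly improved after taking 2mg of sirolimus once a day for three months, the initial administration should be continued". Otherwise, "If the condition of a subject shows no significant improvement, the dosage should be changed into 2.5mg-3mg once a day". A patient who cannot tolerate the higher dose leaves the study.
- **Start of dosing (VI.1).** Sirolimus begins "since the fifth to seventh day of menstruation".
- **Eligibility and exit.** Participants are menstruating adults. Pregnancy bars entry under both V.A.7 and V.B.1. V.C does not name pregnancy as a reason for exit, but has general clauses on safety and on harm to health.

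**The concern.** Month 3 is the scheduled point at which a patient on 2 mg is either given a second three months at that dose or moved to a higher one. A plan followed as written asks whether she has improved and whether she tolerates the drug. It does not ask whether she still meets the condition that would have kept her out at entry.

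Conception on treatment is foreseeable. The patients menstruate, the background section presents preserving fertility as a reason for the research, and the visible text contains no contraception requirement.

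There is also a consequence for the outcome. Section III makes symptom control at 3 and 6 months a study result, and heavy menstrual bleeding is a qualifying symptom under V.A.2. If menses stop because of an unrecognised conception, the patient could be judged improved and kept on 2 mg. The opposite error is also possible: V.A.2 admits patients on pelvic pressure or pain alone, and a pregnant patient whose pressure persists could be judged unimproved and have her dose raised.

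**Working it through.** The plan states no figure to reproduce. The check sets the schedule beside the dose rule and then sizes the interval without a named test.

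**Schedule, for a six-month course**

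| Time | Pregnancy test named? | Source |
|---|---|---|
| Baseline | Yes | VIII.1, item 7 |
| Month 3 | No | VIII.2 |
| End of therapy (month 6) | Yes, by reference | VIII.3 |
| 6 and 12 months after | Yes, by reference | VIII.3 |

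A patient who stops at month 3 is tested then under VIII.3. The gap concerns only patients who go on.

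**Before dosing.** Baseline tests may be up to four weeks old at the first dose, but VI.1 ties that dose to days 5-7 of menstruation. That window is left out, and only conception on treatment is considered.

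**Interval and doses.** Assumptions: three months is about 13 weeks, and one dose is taken daily.

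- Doses to month 3: 13 × 7 = 91.
- Doses in six months: 26 × 7 = 182.
- Doses after the month-3 decision: 182 − 91 = 91.
- Longest run of dosing without a named test: 26 weeks as written, 13 weeks with a month-3 test.

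**Ceiling on drug given after month 3 if a pregnancy is missed there**

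- Continued at 2 mg: 91 × 2 = 182 mg.
- Raised to 2.5 mg: 91 × 2.5 = 227.5 mg, about 228 mg.
- Raised to 3 mg: 91 × 3 = 273 mg.

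These ceilings require the pregnancy to go unnoticed for the whole second period. They say nothing about how likely that is.

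**Effect on the outcome.** With the minimum of 25 patients in the denominator, one pregnancy misread as symptom control moves the rate by 1/25 = 4 percentage points. The documents give no basis for an expected number of such patients.

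**Cost.** 25 patients × 1 test = 25 dipsticks at the minimum sample size, or fewer if some stop at month 3 and are tested under VIII.3 anyway.

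**The case against.** The strongest reply is that the month-3 visit is not blind to pregnancy. The uterus is measured by MRI, female hormones are drawn, endometrial thickness is monitored, and bleeding is enquired about. For a pregnancy to pass as improvement, or as persisting disease, all of these would have to miss it. This stands for an established pregnancy. It is weaker for a conception shortly before the visit. VIII.2 also does not name hCG, and nothing in VI.2 makes the dose depend on excluding pregnancy. Unspecified laboratory values permit a test without requiring one.

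Second, the flow chart in section VII is not shown and the consent pages were removed. Either could list a test, so absence can be claimed only for the visible text. This stands in full.

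Third, one extra dipstick prevents no conception and still leaves two runs of about 13 weeks. This is fair: the test is placed at month 3 because a dosing decision is made there, not because 13 weeks is a proven safe interval.

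A reader might infer more than the documents support:

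- *No testing after baseline.* VIII.3 restores the test at end of therapy and twice afterwards.
- *A known pregnancy would not lead to withdrawal.* The general clauses in V.C cover it; the gap is in detection.
- *Pregnant patients would typically receive 91 more doses.* That figure is a maximum.
- *A stated fetal hazard is being ignored.* The documents describe no specific risk of sirolimus in pregnancy; the point rests on the protocol's own entry rule.
- *VI.2 governs everyone treated past three months.* Its continuation rule is written for patients on 2 mg. VI.1 allows reduction to as little as 1 mg a day, and what those patients continue on is not clear.

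**Conclusion.** The point holds as an omission in the visible text, not as a contradiction. No pregnancy test is named between baseline and end of therapy, so the month-3 decision can be taken without excluding a condition that bars entry. The main residual is an early conception that imaging, hormone levels and endometrial monitoring do not show.

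The size that can be stated is the interval: about 26 weeks of dosing without a named test, against about 13 with one at month 3. The number of pregnancies affected cannot be estimated. No sample-size figure or analysis rule changes. The change is worth making because it is cheap, protects participants and guards the symptom-control outcome. The verdict assumes that the section VII flow chart does not already list the test and that therapy ends at month 6.

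**What to change.** First check the section VII flow chart. If it does not already include the test:

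- **VIII.2:** add the baseline urine pregnancy test to the month-3 evaluation, done before the MRI and the dose decision.
- **VI.2:** require a negative result before sirolimus is continued at any dose, including a reduced one, or raised. Stop sirolimus if the result is positive.
- **Outcome definition:** state that stopped menses in a pregnant patient do not count as symptom control.

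No addition is needed at month 6, where VIII.3 supplies the test for patients whose therapy ends then. Two optional additions are to name pregnancy among the exit criteria in V.C, and to repeat the test at visits of rare-type patients who stay on the drug under VI.4, although that may be care outside the study.

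The cost is one dipstick per patient at a visit already scheduled, 25 at the minimum sample size, and a line of text in each place.

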### 2. Evaluation during sirolimus treatment

In the first month of treatment, evaluation of adverse reactions is conducted every week. In the third and sixth months, curative effects and safety of sirolimus were assessed.

1) Evaluation of curative effects: sizes of the uterus and fibroids were measured through pelvic MRI. Blood was drawn to monitor the female hormone level and impacts of bleeding and symptoms on daily life of subjects.

2) Evaluation of safety: safety parameters (such as to enquire AE and measure laboratory values, vital signs, thickness of endometrium, abnormal uterine bleeding and sizes of follicular structure including follicle and functional ovarian cysts) are monitored periodically during the study.

3) Treatment compliance: in order to monitor compliance, subjects are asked to keep an E-diary every day. Researchers track each date of studied drug taking in accordance with E-diaries. In each interview, researchers and subjects examine the data integrity of E-diaries together.

